11.6 Appendix 6. Sample Storage and Destruction

Any blood and tumor sample collected according to the Schedule of Activities (Section 1.3) can be analyzed for any of the tests outlined in the protocol and for any tests necessary to minimize risks to study subjects. This includes testing to ensure analytical methods produce reliable and valid data throughout the course of the study. This can also include, but is not limited to, investigation of unexpected results, incurred sample reanalysis, and analyses for method transfer and comparability.

All samples and associated results will be coded prior to being shipped from the site for analysis or storage. Samples will be tracked using a unique identifier that is assigned to the samples for the study. Results are stored in a secure database to ensure confidentiality.

analysis are to be documented and maintained, but are not necessarily reported as part of this study. Samples can be retained for up to 20 years.

The subject retains the right to request that the sample material be destroyed by contacting the investigator. Following the request from the subject, the investigator is to provide the sponsor with the required study and subject number so that any remaining blood or tumor samples and any other components from the cells can be located and destroyed. Samples will be destroyed once all protocol-defined procedures are completed. However, information collected from samples prior to the request for destruction, will be retained by Amgen.

The sponsor is the exclusive owner of any data, discoveries, or derivative materials from the sample materials and is responsible for the destruction of the sample(s) at the request of the subject through the investigator, at the end of the storage period, or as appropriate (eg, the scientific rationale for experimentation with a certain sample type no

Protocol Number: 20200392

Date: 28 April 2022 Page 126 of 149

longer justifies keeping the sample). If a commercial product is developed from this research project, the sponsor owns the commercial product. The subject has no commercial rights to such product and has no commercial rights to the data, information, discoveries, or derivative materials gained or produced from the sample. See Section 11.3 for subject confidentiality.

Protocol Number: 20200392

Date: 28 April 2022 Page 127 of 149

11.7 Appendix 7. Hepatotoxicity Stopping Rules: Suggested Actions and Follow-up Assessments and Study Treatment Rechallenge Guidelines

Subjects with abnormal hepatic laboratory values (ie, alkaline phosphatase [ALP], aspartate aminotransferase [AST], alanine aminotransferase [ALT], total bilirubin [TBL]) and/or international normalized ratio (INR) and/or signs/symptoms of hepatitis (as described below) may meet the criteria for withholding or permanent discontinuation of Amgen investigational product or other protocol-required therapies, as specified in the *Guidance for Industry Drug-Induced Liver Injury: Premarketing Clinical Evaluation, July 2009.*

Criteria for Withholding and/or Permanent Discontinuation of Amgen Investigational Product and Other Protocol-required Therapies Due to Potential Hepatotoxicity

The following stopping and/or withholding rules apply to subjects for whom another cause of their changes in liver biomarkers (TBL, INR and transaminases) has not been identified.

Important alternative causes for elevated AST/ALT and/or TBL values include, but are not limited to:

- Hepatobiliary tract disease
- Viral hepatitis (eg, hepatitis A/B/C/D/E, Epstein-Barr Virus, cytomegalovirus, herpes simplex virus, varicella, toxoplasmosis, and parvovirus)
- Right sided heart failure, hypotension or any cause of hypoxia to the liver causing ischemia
- Exposure to hepatotoxic agents/drugs or hepatotoxins, including herbal and dietary supplements, plants and mushrooms
- Heritable disorders causing impaired glucuronidation (eg, Gilbert's syndrome, Crigler-Najjar syndrome) and drugs that inhibit bilirubin glucuronidation (eg, indinavir, atazanavir)
- Alpha-one antitrypsin deficiency
- Alcoholic hepatitis
- Autoimmune hepatitis
- Wilson's disease and hemochromatosis
- Nonalcoholic fatty liver disease including steatohepatitis
- Non-hepatic causes (eg, rhabdomyolysis, hemolysis)

Protocol Number: 20200392

Date: 28 April 2022 Page 128 of 149

If investigational product(s) is/are withheld, the subject is to be followed for possible drug induced liver injury (DILI) according to recommendations in the last section of this appendix.

Rechallenge may be considered if an alternative cause for impaired liver tests (ALT, AST, ALP) and/or elevated TBL, is discovered and the laboratory abnormalities resolve to normal or baseline (see next section in this appendix).

Table 11-3. Conditions for Withholding and/or Permanent Discontinuation of Amgen Investigational Product and Other Protocol-required Therapies Due to Potential Hepatotoxicity

| Analyte | Temporary Withholding | Permanent Discontinuation |
|---------|--|--|
| TBL | > 3x ULN at any time | > 2x ULN |
| | | OR |
| INR | | > 1.5x (for subjects not on anticoagulation therapy) |
| | OR | AND |
| AST/ALT | > 8x ULN at any time > 5x ULN but < 8x ULN for ≥ 2 weeks > 5x ULN but < 8x ULN and unable to adhere to enhanced monitoring schedule > 3x ULN with clinical signs or symptoms that are consistent with hepatitis (such as right upper quadrant pain/tenderness, fever, nausea, vomiting, and jaundice) | In the presence of no important alternative causes for elevated AST/ALT and/or TBL values > 3x ULN (when baseline was < ULN) |
| | OR | |
| ALP | > 8x ULN at any time | |

ALP = alkaline phosphatase; ALT = alanine aminotransferase; AST = aspartate aminotransferase; INR = international normalized ratio; TBL = total bilirubin; ULN = upper limit of normal

Criteria for Rechallenge of Amgen Investigational Product and Other Protocol-required Therapies After Potential Hepatotoxicity

The decision to rechallenge the subject is to be discussed and agreed upon unanimously by the subject, investigator, and Amgen.

If signs or symptoms recur with rechallenge, then AMG 176 is to be permanently discontinued. Subjects who clearly meet the criteria for permanent discontinuation (as described in Table 11-2) are never to be rechallenged.

Protocol Number: 20200392

Date: 28 April 2022 Page 129 of 149

Drug-induced Liver Injury Reporting and Additional Assessments

Reporting

To facilitate appropriate monitoring for signals of DILI, cases of concurrent AST or ALT and TBL and/or INR elevation, according to the criteria specified in the above, require the following:

- The event is to be reported to Amgen as a serious adverse event within 24 hours of discovery or notification of the event (ie, before additional etiologic investigations have been concluded)
- The appropriate Case Report Form (CRF) (eg, Events CRF) that captures information necessary to facilitate the evaluation of treatment-emergent liver abnormalities is to be completed and sent to Amgen

Other events of hepatotoxicity and potential DILI are to be reported as serious adverse events if they meet the criteria for a serious adverse event defined in Section 11.4.

Additional Clinical Assessments and Observation

All subjects in whom investigational product(s) or protocol-required therapies is/are withheld (either permanently or conditionally) due to potential DILI as specified in Table 11-2 or who experience AST or ALT elevations > 3 x upper limit of normal (ULN) or 2-fold increases above baseline values for subjects with elevated values before drug are to undergo a period of "close observation" until abnormalities return to normal or to the subject's baseline levels.

Assessments that are to be performed during this period include:

- Repeat AST, ALT, ALP, bilirubin (BIL) (total and direct), and INR within 24 hours
- In cases of TBL > 2x ULN or INR > 1.5, retesting of liver tests, BIL (total and direct), and INR is to be performed every 24 hours until laboratory abnormalities improve

Testing frequency of the above laboratory tests may decrease if the abnormalities stabilize or the investigational product(s) or protocol-required therapies has/have been discontinued AND the subject is asymptomatic.

Initiate investigation of alternative causes for elevated AST or ALT and/or elevated TBL. The following are to be considered depending on the clinical situation:

- Complete blood count with differential to assess for eosinophilia
- Serum total immunoglobulin (Ig)G, anti-nuclear antibody anti-smooth muscle antibody, and liver kidney microsomal antibody-1 to assess for autoimmune hepatitis
- Serum acetaminophen (paracetamol) levels
- A more detailed history of:

Protocol Number: 20200392

Date: 28 April 2022 Page 130 of 149

Prior and/or concurrent diseases or illness

- Exposure to environmental and/or industrial chemical agents
- Symptoms (if applicable) including right upper quadrant pain, hypersensitivity-type reactions, fatigue, nausea, vomiting and fever
- Prior and/or concurrent use of alcohol, recreational drugs and special diets
- Concomitant use of medications (including non-prescription medicines and herbal and dietary supplements), plants, and mushrooms
- Viral serologies
- Creatine phosphokinase, haptoglobin, lactate dehydrogenase and peripheral blood smear
- Appropriate liver imaging if clinically indicated
- Appropriate blood sampling for pharmacokinetic analysis if this has not already been collected
- Hepatology consult (liver biopsy may be considered in consultation with a hepatologist)

Follow the subject and the laboratory tests (ALT, AST, TBL, INR) until all laboratory abnormalities return to baseline or normal or considered stable by the investigator. The "close observation period" is to continue for a minimum of 4 weeks after discontinuation of all investigational product(s) and protocol-required therapies.

The potential DILI event and additional information such as medical history, concomitant medications and laboratory results must be captured in the corresponding CRFs.

Protocol Number: 20200392

Date: 28 April 2022 Page 131 of 149

11.8 Appendix 8. Protocol-specific Anticipated Serious Adverse Events

Anticipated serious adverse events are events that are anticipated to occur in the study population at some frequency independent of investigational product exposure and do not need to be reported individually as an FDA IND safety report by the sponsor. Identification and reporting of anticipated serious adverse events is the responsibility of the sponsor; the investigator is responsible for reporting adverse events and serious adverse events as described in Appendix 11.4.

Anticipated Serious Adverse Events for Study 20200392.02

| Preferred Term ¹ |
|------------------------------------|
| Acute myeloid leukaemia |
| Acute myeloid leukaemia recurrent |
| Acute myeloid leukaemia refractory |
| Neutropenia |
| Anaemia |
| Thrombocytopenia |
| Leukocytosis |
| Leukopenia |
| White blood cell decreased |
| Hemoglobin decreased |
| Platelet count decreased |
| White blood cell increased |

¹ MedDRA Version 24.0

Protocol Number: 20200392

Date: 28 April 2022 Page 132 of 149

11.9 Appendix 9. Tumor Lysis Syndrome

11.9.1 Cairo-Bishop Tumor Lysis Syndrome Definition and Grading

Common Terminology Criteria for Adverse Events (CTCAE) version 5.0 classifies tumor lysis syndrome (TLS) in grade 3 (present), grade 4 (life threatening consequences; urgent intervention indicated) and grade 5 (death). Presence of TLS is not clearly defined by CTCAE version 5.0. Cairo and Bishop developed a system for defining and grading TLS based on Hande-Garrow classification of laboratory or clinical TLS (Coiffier et al, 2008). For this trial the Cairo-Bishop classification will be used to define presence of TLS, ie, presence of laboratory TLS (see Table 1-1) and clinical TLS (see Table 11-5) including grading as detailed below.

Based on the Cairo and Bishop system, laboratory TLS is present when levels of 2 or more serum values of uric acid, potassium, phosphorus, or calcium are more than or less than normal at presentation or if they change by 25% within 3 days before or 7 days after initiation of treatment (Section 1.3).

Table 11-4. Cairo-Bishop Definition of Laboratory Tumor Lysis Syndrome

| Element | Value | Change from Baseline |
|------------|---|----------------------|
| Uric acid | $\geq 476~\mu mol/L$ or 8 mg/dL | 25% increase |
| Potassium | \geq 6.0 mmol/L or 6 mg/L | 25% increase |
| Phosphorus | \geq 2.1 mmol/L for children or \geq 1.45 mmol/L for adults | 25% increase |
| Calcium | ≤ 1.75 mmol/L | 25% decrease |

Note: Two or more laboratory changes within 3 days before or 7 days after cytotoxic therapy will constitute laboratory tumor lysis syndrome.

Clinical TLS requires the presence of laboratory TLS in addition to 1 or more of the following significant complications: renal insufficiency, cardiac arrhythmias/sudden death, and seizures (Table 11-5). The grade of clinical TLS is defined by the maximal grade of the clinical manifestations as detailed in Table 11-5.

Protocol Number: 20200392

Date: 28 April 2022 Page 133 of 149

Table 11-5. Cairo-Bishop Clinical Tumor Lysis Syndrome Definition and Grading

| Grade | Creatinine ^{a, b} | Cardiac Arrhythmia ^a | Seizure ^a |
|-------|----------------------------|---|--|
| 0 | ≤ 1.5 x ULN | none | none |
| 1 | 1.5 x ULN | intervention not indicated | |
| 2 | > 1.5 – 3.0 x ULN | non urgent medical intervention indicated | one brief, generalized seizure; seizure(s) well controlled by anticonvulsants or infrequent focal motor seizures not interfering with ADL |
| 3 | > 3.0 – 6.0 x ULN | symptomatic and incompletely controlled medically or controlled with device (eg, defibrillator) | seizure in which consciousness is altered; poorly controlled seizure disorder; with breakthrough generalized seizures despite medical intervention |
| 4 | > 6.0 x ULN | life-threatening (eg, arrhythmia associated with CHF, hypotension, syncope, shock) | seizure of any kind which are prolonged, repetitive or difficult to control (eg, status epilepticus, intractable epilepsy) |
| 5 | Death | death | death |

Note: Laboratory TLS and at least 1 clinical complication will constitute clinical TLS.

ADL = activities of daily living; CHF = congestive heart failure; TLS = tumor lysis syndrome, ULN = upper limit of normal

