- Monitoring of electrolyte values is required prior to dosing anytime a dose is higher than one previously given to the subject. This will include at the following times:
 - Prior to the week 1, day 1 dose.
 - Prior to each dose during the lead-in period.
 - Prior to the initial dosing at the target dose level.
- Prior to administering these doses, all electrolyte values (including LDH, potassium, uric acid, phosphorus, calcium, and creatinine) must be reviewed and within normal range (samples must be drawn within 24 hours prior to dosing of AMG 176). The investigator's decision to proceed with AMG 176 treatment initiation will be based on these laboratory values.

Within the first 24 hours after either the first dose or dose escalation, if any laboratory criteria for TLS are met, no additional AMG 176 doses should be administered until resolution. A rapidly rising serum potassium is a medical emergency.

Prophylactic dose reductions for potassium, phosphorus and/or uric acid values at the high end of normal range should be considered.

If the potassium, uric acid, inorganic phosphate and/or creatinine values are higher than the normal range or the calcium is lower or higher than the normal range, this (these) value(s) can be approved following a discussion between the Amgen Medical Monitor and investigator.

On the AMG 176 dosing days chemistry labs must be performed pre-dose (within 4 hours before AMG 176 administration), 2, 4, 8, 12, and 24 hours after the start of AMG 176 infusion. Pre-dose labs will be used as baseline to assess potential electrolytes abnormalities occurring post AMG 176 administration. These labs must be reviewed in real time by the investigator.

All 24-hour laboratory assessments may be taken \pm 2 hours, if necessary.

Monitor for signs and symptoms of TLS (eg, fever, chills, tachycardia, nausea, vomiting, diarrhea, diaphoresis, hypotension, muscle aches, weakness, paresthesias, mental status changes, confusion, and seizures). If any clinical features are observed, recheck potassium, phosphorus, uric acid, calcium, and creatinine within 1 hour.

Additional information on the management recommendations of laboratory abnormalities can be found in Section 11.2.

 Nephrology (or acute dialysis service) consultation should be considered on admission (based on investigator discretion) for hospitalized subjects per

Protocol Number: 20200392

Date: 28 April 2022 Page 56 of 149

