- Prophylactic dose reductions for potassium, phosphorus and/or uric acid values at the high end of normal range should be considered.
- If the potassium, uric acid, inorganic phosphate and/or creatinine values are higher than the normal range or the calcium is lower or higher than the normal range, this (these) value(s) can be approved following a discussion between the Amgen medical monitor and investigator.
- On the AMG 176 dosing days chemistry labs must be performed pre-dose (within 4 hours before AMG 176 administration), 2, 4, 8, 12, and 24 hours after the start of AMG 176 infusion. Pre-dose labs will be used as baseline to assess potential electrolytes abnormalities occurring post AMG 176 administration. These labs must be reviewed in real time by the investigator.
- All 24-hour laboratory assessments may be taken ± 2 hours, if necessary.
- Perform hematology labs at pre-dose (within 4 hours before AMG 176 administration) and 24 hours after the start of AMG 176 infusion.
- Monitor for signs and symptoms of TLS (eg, fever, chills, tachycardia, nausea, vomiting, diarrhea, diaphoresis, hypotension, muscle aches, weakness, paresthesias, mental status changes, confusion, and seizures). If any clinical features are observed, recheck potassium, phosphorus, uric acid, calcium and creatinine within 1 hour.
- Nephrology (or acute dialysis service) consultation should be considered on admission (based on investigator discretion) for hospitalized subjects per institutional guidelines to ensure emergency dialysis is available and the appropriate staff is aware and prepared.

All subjects will receive TLS prophylaxis as described above. Allopurinol or equivalent should be used to reduce uric acid level. This should be initiated at least 72 hours prior to dosing. Treatment may need to be continued for up to 5 weeks. Other agents to reduce uric acid level, such as rasburicase, may be used per investigator discretion and institutional guidelines.

Within the first 24 hours after either the first dose or dose escalation, if any laboratory criteria below are met, no additional AMG 176 doses or azacitidine should be administered until resolution. A rapidly rising serum potassium is a medical emergency.

Nephrology (or other acute dialysis service) should be contacted/consulted (per institutional guidelines to ensure emergency dialysis is available) on admission for any subject hospitalized prophylactically or in response to laboratory changes.

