Abnormality Management Recommendations Hyperkalemia (including rapidly rising potassium) • Potassium ≥ 0.5 mmol/L • Recheck potassium, phosphorus, uric acid, calcium and creatinine in 1-hour STAT. If further ≥ 0.2 mmol/L increase from prior value (even if potassium within increase in potassium, but still < upper limit of normal normal limits [WNL]) (ULN), manage as per potassium ≥ ULN. Otherwise recheck in 1 hour. • Resume per protocol testing if change in potassium is < 0.2 mmol/L, and potassium < ULN, and no other evidence of tumor lysis. • At discretion of Investigator, may recheck prior to hospitalization. If stable or decreased, and still WNL, hospitalization is at discretion of the Investigator. Potassium phosphorus, uric acid, calcium and creatinine must be rechecked within 24 hours. • Potassium > upper limit of Perform STAT ECG and commence telemetry. normal Nephrology notification with consideration of initiating dialysis. Administer Kayexalate 60 g (or Resonium A 60 g). Administer furosemide 20 mg IV x 1 • Administer calcium gluconate 100 - 200 mg/kg IV slowly if there is ECG/telemetry evidence of life-threatening arrhythmias. • Recheck potassium, phosphorus, uric acid, calcium and creatinine in 1 hour STAT. If potassium < ULN 1 hour later, repeat potassium phosphorus, uric acid, calcium and creatinine 1, 2, and 4 hours, if no other evidence of tumor lysis. • Potassium ≥ 6.0 mmol/L • Perform STAT ECG and commence telemetry. (6.0 mEg/L) and/or • Nephrology (or other acute dialysis service) assessment symptomatic (eg, muscle with consideration of initiating dialysis. cramps, weakness, Administer Kayexalate 60 g (or Resonium A 60 g). paresthesias, nausea, Administer furosemide 20 ma IV x 1. vomiting, diarrhea) Administer insulin 0.1 U/kg IV + D25 2 mL/kg IV. Administer sodium bicarbonate 1 to 2 mEq/kg IV push. If sodium bicarbonate is used, rasburicase should not be used as this may exacerbate calcium phosphate precipitation. Administer calcium gluconate 100 to 200 mg/kg IV slowly if there is ECG/telemetry evidence of life-threatening arrhythmias. Do not administer in same IV line as sodium bicarbonate. Recheck potassium, phosphorus, uric acid, calcium and creatinine every hour STAT.

Page 1 of 3

Protocol Number: 20200392

Date: 28 April 2022 Page 138 of 149

Table 11-6. Tumor Lysis Syndrome Management Recommendations

| Hyperuricemia | |
|--|--|

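### The Section 11.9.1 text on laboratory tumor lysis syndrome contradicts Table 11-4, its pointer goes to the wrong table, and Section 11.9.3 gives two different hold rules

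*Protocol*

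**What the plan says.** **Definition.** Protocol Section 11.9.1 sets a two-analyte rule in its text: "laboratory TLS is present when levels of 2 or more serum values of uric acid, potassium, phosphorus, or calcium". To count, according to the rest of that sentence, the levels must be ones that "are more than or less than normal at presentation or if they change by 25" percent; the window runs from 3 days ahead of treatment to 7 days after it starts. Table 11-4 follows. It gives fixed limits for the same four analytes and a directional change for each: an increase for uric acid, potassium and phosphorus, a decrease for calcium. Its note reads: "Two or more laboratory changes within 3 days before or 7 days after cytotoxic therapy will constitute laboratory tumor lysis syndrome".

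**Pointer.** The same section directs the reader to the definitions with "presence of laboratory TLS (see Table 1-1) and clinical TLS (see Table 11-5". Table 1-1 is the Part 1A, Cycle 1 Schedule of Activities.

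**Hold rules.** For the first 24 hours after a first dose or a dose escalation, Section 6.1.4.1 says "if any laboratory criteria for TLS are met, no additional AMG 176 doses should be administered until resolution", and a bullet in Section 11.9.3 repeats it. Later in Section 11.9.3 a second sentence covering the same 24 hours says "if any laboratory criteria below are met, no additional AMG 176 doses or azacitidine should be administered until resolution". The only laboratory limits printed after that second sentence are the management triggers of Table 11-6. One of them begins "Potassium ≥ 0.5 mmol/L". The row makes clear that this is a rise, not a level, and that it applies even when the value stays in the normal range: "increase from prior value (even if potassium within".

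**The concern.** Section 11.9.1 exists because CTCAE does not clearly define when TLS is present, so it should give one rule. Its text and its table agree that two analytes are needed but disagree on what counts for each. The cross-reference that should settle the matter leads to a visit schedule.

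The hold is a safety instruction for an identified risk that has already had a fatal outcome (Section 2.3.2). As written, the trigger may be the TLS criteria or the wider list in Table 11-6. The drugs held may be AMG 176 alone or AMG 176 with azacitidine. Neither sentence says whether one criterion or two are needed.

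The definition also has a downstream use: clinical TLS requires laboratory TLS, and the TLS line of the DLT criteria in Table 6-2 refers to Section 11.9.1.

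**Working it through.** The plan states no figure to reproduce. The check sets the rules side by side and scores a few laboratory profiles against them. All patient values are illustrative assumptions. Baselines are taken as normal and unlisted analytes as stable. Table 11-4 prints no connective between its two columns, so they are read as alternatives unless noted.

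| Item | Section 11.9.1 text | Table 11-4 |
|---|---|---|
| Analytes needed | 2 or more | 2 or more |
| Level criterion | outside normal, either direction, at presentation | uric acid ≥ 8 mg/dL; potassium ≥ 6.0 mmol/L; adult phosphorus ≥ 1.45 mmol/L; calcium ≤ 1.75 mmol/L |
| Change criterion | 25%, no direction | 25% increase (uric acid, potassium, phosphorus); 25% decrease (calcium) |

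Percent change = (later − baseline) / baseline.

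**Profile A: the text counts, the table does not.**
- Uric acid 6.0 to 4.0 mg/dL: (4.0 − 6.0)/6.0 = −33.3%.
- Phosphorus 1.10 to 0.80 mmol/L: (0.80 − 1.10)/1.10 = −27.3%.
- Text: two analytes have changed by at least 25%, so laboratory TLS is present.
- Table 11-4: 25% increases would be 6.0 × 1.25 = 7.5 mg/dL and 1.10 × 1.25 = 1.375 mmol/L, and both values are below the fixed limits. Zero criteria are met.

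**Profile B: the table counts, the text does not.**
- Potassium 5.0 to 6.0 mmol/L: 1.0/5.0 = +20.0%. Phosphorus 1.3 to 1.5 mmol/L: 0.2/1.3 = +15.4%.
- Table 11-4: both fixed limits are met (6.0 ≥ 6.0; 1.5 ≥ 1.45), so laboratory TLS is present. If both columns were required, the count would be zero.
- Text: neither change reaches 25%, and the values were normal at presentation. Zero criteria are met.

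**Profile C: the hold sentences differ.**
- Potassium 4.0 to 4.6 mmol/L: +0.6 mmol/L, 0.6/4.0 = +15.0%.
- First sentence (TLS criteria): no hold. Table 11-4 needs ≥ 6.0 mmol/L or a 25% rise to 4.0 × 1.25 = 5.0 mmol/L, and the text also needs a 25% change.
- Second sentence (criteria below): the Table 11-6 potassium row is met because 0.6 ≥ 0.5, so on its face both drugs are held. That row's own action is a one-hour recheck, with no hold.

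**Profile D: creatinine up 25%, nothing else.** This meets a Table 11-6 row whose action is fluids and a recheck. Creatinine is not among the four analytes in the text or in Table 11-4.

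**Profile E: one criterion or two.**
- Phosphorus 1.10 to 1.50 mmol/L: 0.40/1.10 = +36.4%. One Table 11-4 analyte is met, so this is not laboratory TLS.
- First sentence: AMG 176 is held if one criterion is enough, and not held if laboratory TLS is meant.
- Second sentence: no hold, because the Table 11-6 phosphorus row starts at 1.615 mmol/L.

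**The case against.** Much of the case on the other side stands.

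- **Intended definition.** Section 11.9.1 adopts the Cairo-Bishop classification, and Table 11-4 carries that name in its title directly under the text. A careful site would use the table and would not diagnose tumor lysis from falling values, especially as uric-acid-lowering prophylaxis is to start at least 72 hours before dosing. The contradiction is real, but the documents do not support the inference that the definition is undeterminable.
- **Normal values before dosing.** Electrolytes must be in range before dosing unless the medical monitor and investigator agree otherwise. This narrows the branch that counts abnormal values at presentation.
- **Baseline.** A reader might infer that the baseline for a 25% change is missing. It is not: Sections 6.1.4.1 and 11.9.3 both make the pre-dose labs the baseline.
- **Compatible holds.** The hold sentences do not force a choice. Neither says azacitidine must continue, so a site can obey both by holding whatever either one requires. The usual meaning of any criteria is one or more, which is also the cautious reading. What remains is that the wider sentence attaches a hold to rows written for rechecks.
- **Evaluability.** A reader might infer from Profile C that a day-2 azacitidine dose is lost, leaving 6/7 = 85.7% of cycle 1 doses against the 100% needed for DLT-evaluability. That requires the delayed dose never to be given. Table 11-6 calls for a recheck within an hour, and the hold lasts only until resolution, so a short delay is at least as plausible.
- **DLT counts.** The TLS criterion in Table 6-2 requires clinical TLS of grade 3 or higher that has not resolved to grade 2 or lower within 7 days. The definition feeds into it, but a changed count would be rare.

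**Conclusion.** The point holds in limited form. The Section 11.9.1 text contradicts Table 11-4 and, read literally, counts harmless falls in uric acid and phosphorus as laboratory TLS. The Table 1-1 pointer is wrong. Section 11.9.3 holds different drugs on different triggers, and the wider trigger reaches Table 11-6 rows that were not written as holds.

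Severity is low minor. The profiles show that the rules can disagree; they do not show how often. The Profile B result rests on reading the Table 11-4 columns as alternatives. The difference in drugs held cannot arise in Part 1A, which gives no azacitidine. Effects on azacitidine delivery, DLT-evaluability or DLT counts are possible but speculative. No sample size, power or planned estimate is affected. The SAP reports early termination and that Part 2 did not enroll (Sections 3.1 and 7.1), so the remaining value lies in consistent classification in the adverse event and DLT listings (SAP Section 9.6.2) and in any reuse of this text.

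**What to change.** 1. Make Table 11-4 the sole definition of laboratory TLS and rewrite the Section 11.9.1 sentence to its cut-offs and directions. State whether its two columns are alternatives.
2. Correct the pointer from Table 1-1 to Table 11-4.
3. Replace the hold sentences in Sections 6.1.4.1 and 11.9.3 with one sentence, used in both places, that cites Table 11-4, states whether one or two criteria trigger the hold, and names the drugs held.
4. Keep Table 11-6 as management guidance unless the sponsor's clinicians designate a particular row as a hold trigger. The limits themselves are for them to choose.

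The cost is a wording change in Appendix 9 and Section 6.1.4.1, with no added procedures or samples.
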